1.2 PRECIS

Arboviral epidemics continue to emerge suddenly and spread of disease is unpredictable. The 2015-16 Zika epidemic resulted in a high case number in Thailand, but not in neighboring Cambodia. It is known that nonhuman primates (NHPs) are important reservoirs of arboviruses, but the importance of their

epidemiological role in the transmission of arboviruses is not clearly understood. While transmission dynamics are complex and require consideration of many variables, primate reservoirs are not routinely sampled, particularly in Southeast Asia, because of the level of operational complexity and skill required.

Here, we propose a serological survey for evidence of Zika virus (ZIKV), dengue virus (DENV), and chikungunya virus (CHIKV) exposure in long-tailed macaques and human adults who live or work in close proximity to these monkeys in Thailand and Cambodia. We hypothesize that ZIKV seroprevalence in both humans and macaques will be higher in Thailand than Cambodia. With the current rise of arboviral diseases around the world, we hope the results of this study contribute to better understanding of the epidemiology and burden of arboviral diseases in this region.

Schema 1: Study Flow Design

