4 STUDY DESIGN

4.1 SITE DESCRIPTION

Located in Cambodia, the main town of Chbar Mon (estimated population approximately 55,000-60,000 over 10 km²) is located 44 km from Phnom Penh city center. Chbar Mon is the largest operational district in Kampong Speu province and is the site of the Kampong Speu District Referral Hospital, a hospital of approximately 120 beds with 130 staff of medical doctors, nurses, and lab technicians. NIAID has a field house behind the hospital that serves as an office and temporary clinic when needed.

Wat Amphae Phnom is a pagoda next to a river tributary of the Mekong with 3 different macaque troops, numbering over 75 to 100 per troop. Similar to the sites in Thailand, the pagoda is a popular tourist destination where locals purchase food from vendors to feed the monkeys and also hosts a local marketplace and restaurants (called Resort Amphae Phnom). Over 100 monks also live at the pagoda. The closest residences are in the section of town called Taing Toun Le, where NIAID already has many children enrolled in a healthy pediatric cohort.

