9 STATISTICAL CONSIDERATIONS

9.1 STATISTICAL HYPOTHESES

We hypothesize that seroprevalence as measured via ZIKV PRNT50 titers will be lower in Cambodian human adults and macaques compared to Thai human adults and macaques.

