9.2 SAMPLE SIZE JUSTIFICATION AND ANALYSIS PLAN

Though we will also be assessing DENV and CHIKV in humans and monkeys, the following statistical plan is primarily guided by the anticipated ZIKV seroprevalence for two reasons. First, DENV has hyperendemic transmission in both Thailand and Cambodia. Therefore, we expect that sample sizes that are adequate for ZIKV will also be adequate for dengue. Second, CHIKV is known to have sporadic and highly focal transmission in both countries, but there is not enough information to develop reasonable assumptions about the expected prevalence. All sites in Thailand and Cambodia have had documented ZIKV transmission in the past.^{3,18}

As there are limited data available for the seroprevalence of these arboviruses in macaques in Southeast Asia, we based our assumptions about seroprevalence on a field study in Senegal that identified seroprevalence of CHIKV in three species of monkeys.¹⁹ This study found that the seroprevalence across all three species was high, 72% (479/667). There are no studies evaluating ZIKV seroprevalence in macaques in Southeast Asia, only scattered reports from Malaysia, Brazil, and Africa that focused detection on active viremia, though an African study noted 16% seroprevalence of ZIKV.^{6,20,21} Preliminary analyses from our Thai collaborators show that an initial screen for pan-flavivirus antibodies in the Thai macaques is nearly 100% positive ([name], Mahidol University, personal communication). Treating sampled macaques as mutually independent simple random samples of binary responses for seropositivity to a given arbovirus, a sample of 100 monkeys per site will yield an average 95% confidence interval (CI) width of less than or equal to 0.2 for seroprevalence at each site, and we will have 80% power to detect a 25% relative reduction in seroprevalence relative to a site where seroprevalence is 75% using a binomial test of proportions with a Type-1 error rate of 0.05.

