With regards to the sample size in humans, Thailand and Cambodia have both been endemic for dengue for many years. Only recently has ZIKV been actively detected in both countries.^{18,22-24} In Thailand, a serosurvey in a sample of 21 humans estimated ZIKV seroprevalence to be 76% (95% CI: 52%, 91%).²⁵ Another survey of 600 migrant workers from four Southeast Asian countries, 150 of whom were from Thailand, estimated overall seroprevalence to be 38.8% and seroprevalence among the Thai cohort to be 50.7%.²⁶ However, in Cambodia, the estimated seroprevalence was lower, estimated to be <1% definitively with 37.3% equivocal results.⁸ These equivocal results were based on a potentially cross-reactive IgM assay and indicated a recent flavivirus infection with either Japanese encephalitis virus (JEV), DENV, or ZIKV. Treating sampled humans as mutually independent simple random samples of binary responses for seropositivity, a sample of 300 humans in Cambodia will yield an average 95% CI width of less than or equal to 0.052 for presumed seroprevalence centered at 0.05 (Figure 2).

Our secondary objective is to compare human ZIKV seroprevalence in Cambodia with ZIKV seroprevalence in Thailand. Conservatively taking a value of 50% seroprevalence for ZIKV in Thailand and 37% seroprevalence in Cambodia, we calculate that a sample size of N=300 Cambodian participants and N=300 Thai participants will be sufficient to attain 90% power to reject a null hypothesis of no difference in seroprevalence using a binomial test of proportions with a Type-1 error rate of 0.05.

[figure not shown]

Figure 2. Expected precision of seroprevalence estimate versus sample size and true seroprevalence

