9.3.2 ANALYSIS OF THE SECONDARY ENDPOINT

The secondary endpoints will be defined as

- Comparative assessment of seroprevalence via PRNT50 titers for ZIKV, DENV, and CHIKV in Cambodian adults and macaques to that of Thai adults and macaques.
- Assessment of reactivity to salivary gland homogenate of *Aedes aegypti* as detected by ELISA or western blot in human and macaque sera.

Differences in seroprevalence will be assessed via a two-sample test of binomial proportions, treating participants and each study sample as mutually independent of one another. Pairwise comparisons of PRNT50 titers as continuous variables will be assessed via Wilcoxon rank sum tests as follows: Thai adults versus Cambodian adults, Thai macaques versus Cambodian macaques, and Thai adults and macaques versus Cambodian adults and macaques.

For salivary gland reactivity, arbitrary ELISA units as a continuous variable will be assessed and categories will be made for high, medium, low, and negligible reactivity to salivary gland homogenate. These categories will be compared as: Thai adults versus Cambodian adults, Thai macaques versus Cambodian macaques, and Thai adults and macaques versus Cambodian adults and macaques. Regression models fit via generalized estimating equations will be used to assess if higher antibody reactivity is associated with PRNT50 titer and positive/negative seroprevalence of ZIKV, DENV, or CHIKV.

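### The third country comparison in section 9.3.2 pools humans and macaques without stratifying by species, so it can reject with no country difference in either species if the species differ and the human:macaque ratio differs between countries (minor, secondary analysis only)

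*Combined protocol and SAP*

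**What the plan says.** Section 9.3.2 compares PRNT50 titers as continuous variables with Wilcoxon rank sum tests for three pairs: "Thai adults versus Cambodian adults, Thai macaques versus Cambodian macaques, and Thai adults and macaques versus Cambodian adults and macaques". The same three pairs recur for the high/medium/low/negligible salivary categories ("These categories will be compared as: Thai adults versus Cambodian adults", and so on), with no test named. Neither place mentions stratification, weighting or a species term for the third pair. The GEE models later in the section ask whether salivary reactivity is associated with titer or serostatus, so they do not adjust the country comparison.

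For seroprevalence the section says "Differences in seroprevalence will be assessed via a two-sample test of binomial proportions" and lists no pairs. Whether a pooled seroprevalence comparison is intended is therefore open.

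The hypothesis in section 1.2 is worded by species: "We hypothesize that ZIKV seroprevalence in both humans and macaques will be higher in Thailand than Cambodia". Section 9.1 is looser: seroprevalence "will be lower in Cambodian human adults and macaques compared to Thai human adults and macaques".

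On numbers, section 9.2 plans "a sample size of N=300 Cambodian participants and N=300 Thai participants" and, for macaques, "a sample of 100 monkeys per site". Cambodia has one site. Section 4.1 speaks of more than one Thai site ("Similar to the sites in Thailand, the pagoda is a popular tourist destination"). No Thai macaque total appears.

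**The concern.** Pooling species within country mixes two things: any country effect, and the share of each country's sample that is macaque. If macaques and humans have different titer or reactivity distributions, and one country contributes proportionally more macaques, the pooled samples differ even when Thai and Cambodian humans are alike and Thai and Cambodian macaques are alike. A species difference is a live possibility, since comparing the species is itself a primary objective.

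The pooled pair is the only listed comparison that gives a single Thailand-versus-Cambodia answer, and the plan does not say which result governs if the three disagree. At stake is the reading of that one secondary test, for titers and for salivary categories.

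**Working it through.** **1. The plan's own figures.** The two-sided two-proportion power is Φ[(d − 1.96·se0)/se1], where se0 uses the pooled proportion and se1 the separate ones.
- Humans, 50% vs 37%, 300 per country: d = 0.13, se0 = √(2·0.435·0.565/300) = 0.0405, se1 = √((0.25 + 0.2331)/300) = 0.0401. Power is 0.897 (stated 90%).
- Macaques, 75% vs 56.25% (a 25% relative reduction), 100 per site: d = 0.1875, se0 = 0.0672, se1 = 0.0658. Power is 0.802 (stated 80%).

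Both reproduce. Neither covers the pooled pair.

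**2. Why two conditions are needed.** Let qT and qC be the macaque shares of the Thai and Cambodian samples, and θ the probability that a random macaque value exceeds a random human value (ties counted half). With no country effect in either species, the Wilcoxon test targets

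P(Thai > Cambodian) − ½ = (qT − qC)(θ − ½).

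This is zero if the ratios are equal or if the species do not differ in this sense.

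**3. Numbers at a 0.5 SD shift.** θ = Φ(0.5/√2) = 0.638. Assume Cambodia 300:100 (qC = 0.25) and 300 Thai humans. The Thai macaque total is assumed.
- 300 Thai macaques: qT = 0.50, displacement 0.25 × 0.138 = 0.0345. Null SE = √(1001/(12·600·400)) = 0.0186, so z = 1.85 and rejection ≈ Φ(1.85 − 1.96) ≈ 0.46.
- 200 Thai macaques: qT = 0.40, displacement 0.0207, SE = √(901/(12·500·400)) = 0.0194, so z = 1.07 and rejection ≈ 0.19.

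**4. Simulation.** No country difference in either species, α = 0.05. The tied form is assumed: seronegatives share one floor value, and positives have the same log-normal distribution in both species.

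| Pooled Wilcoxon rejection, by Thai macaque total | 100 | 200 | 300 |
|---|---|---|---|
| Normal, no species shift | 5% | 5% | 5% |
| Normal, 0.25 SD | 5% | 8% | 16% |
| Normal, 0.5 SD | 4–5% | 17–18% | 45–46% |
| Normal, 1 SD | 4% | 52% | 95–96% |
| Tied, humans 5% / macaques 16% positive | 4–5% | 14% | 31% |
| Tied, 50% / 75% | 4% | 14–16% | 41% |
| Tied, 37% / 75% | 4% | 34% | 80% |
| Tied, 95% / 98% | 5% | 5% | 6% |

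Repeat simulations of the tied rows agree to within about two points. The van Elteren test (Wilcoxon stratified by species) stays at 4–6% in every row. The percentages in the first three tied rows are planning or cited figures from section 9.2. The last row illustrates a hyperendemic virus such as DENV. There θ − ½ = (0.98 − 0.95)/2 = 0.015, so almost nothing is left to distort. That holds only if titers among positives are similar in the two species; otherwise the shift rows apply.

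**5. Salivary categories.** Four ordered categories cut at the human quartiles, 0.5 SD shift, 100/200/300 Thai macaques. A pooled chi-square test rejects 5%/11%/28% and a pooled trend test 4%/17%/41%. The species-stratified mean-score Cochran-Mantel-Haenszel test stays at about 5%.

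**6. Seroprevalence, if pooled.** At 37% (humans) and 75% (macaques) in both countries, Cambodia pools to (111 + 75)/400 = 46.5%. Thailand with 300 macaques pools to (111 + 225)/600 = 56.0%. The binomial test then rejects with probability 0.855, or 0.390 with 200 Thai macaques and 0.038 with 100.

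**The case against.** The strongest reply is that the design looks balanced. Section 9.2 powers humans at 300 against 300 and macaques as one site of 100 against another. The only macaque-to-macaque comparison in 9.3.2 is Thai versus Cambodian, so the natural reading is 300:100 in both countries, where there is no inflation. This has real weight. It is not decisive, because the Thai sites are plural and the 100 is per site. The Thai work also ran under its own approved protocol, which may state the total. Its absence here is therefore not evidence of imbalance.

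Second, both species-specific pairs are reported alongside, so an attentive reader would see a pooled rejection that neither supports. That limits the harm and stands.

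Third, stratifying recovers little. At 300:100 in both countries, a macaque-only country difference of 0.5 SD (species shift also 0.5 SD) has power 0.33 pooled, 0.39 with van Elteren and 0.93 in macaques alone. This also stands, and it is a reason to rest conclusions on the separate pairs.

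A reader might infer that the plan builds in a false-positive country finding, or that the main ZIKV hypothesis is compromised. The documents support neither. They do not establish unequal ratios. The hypothesis concerns seroprevalence, section 1.2 frames it for each species, and the power statements treat each species separately.

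**Conclusion.** The point holds as a minor one, confined to the pooled pair for titers and salivary categories. That pair can over-reject when both conditions hold: the species differ in distribution, and the human:macaque ratio differs between countries.

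Under the assumption of 200 or 300 Thai macaques against 100 Cambodian, pooled Wilcoxon rejection is about 17% or 45% at a 0.5 SD species shift. With tied titers of the assumed form it is about 14% or 31% at 5% vs 16% positive, and 34% or 80% at 37% vs 75%. It stays at or below about 5% with equal ratios, and near 5% when almost all of both species are positive with similar titers. The Thai macaque total, the species shifts and the form of the titer distribution are assumptions. All figures take observations as independent, as the plan does. This point takes no view on whether that holds within the species-specific comparisons.

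**What to change.** In section 9.3.2, state that country conclusions rest on the two species-specific comparisons. Then do one of the following:
- drop the pooled pair; or
- replace it with a species-stratified test: van Elteren for PRNT50 titers and the mean-score Cochran-Mantel-Haenszel test for the ordered salivary categories. If a combined country comparison of seroprevalence is made, use Cochran-Mantel-Haenszel there too.

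If a stratified version is kept, add that it is read beside the species-specific results, because humans still dominate it and it is a poor detector of an effect confined to macaques.

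The cost is slightly more programming and no new data. Dropping the pair gives up only the single overall country statement. Stratifying loses nothing material if the ratios turn out equal.

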10 SUPPORTING DOCUMENTATION AND OPERATIONAL CONSIDERATIONS

10.1 REGULATORY, ETHICAL, AND STUDY OVERSIGHT CONSIDERATIONS

10.1.1 INFORMED CONSENT PROCESS

10.1.1.1 CONSENT AND OTHER INFORMATIONAL DOCUMENTS PROVIDED TO PARTICIPANTS

ICFs describing in detail the study procedures and risks are given to the participants, and written documentation of informed consent is required prior to starting research procedures and evaluations. The ICFs in English (to be translated into Khmer for submission for Cambodian ethics review and for use in study) are submitted with this protocol.

10.1.1.2 CONSENT PROCEDURES AND DOCUMENTATION

Informed consent is a process where information is presented to enable persons to voluntarily decide whether or not to participate as a research subject. It is an ongoing conversation between the human research subject and the researchers that begins before consent is given and continues until the end of the subject's involvement in the research. Discussions about the research will provide essential information about the study in Khmer and include at the very least the purpose, duration, procedures, alternatives, and risks and benefits. Potential participants will be given the opportunity to ask questions and have them answered. Those who are literate will sign and date the ICF (written in Khmer) prior to undergoing any research procedures. In this case, a witness will not sign and date the ICF. If the potential participant is illiterate, a thumbprint will be obtained and the date will be documented by the investigator. In this case, an impartial witness who is literate and not involved with the study will then sign and date the ICF.

Participants may withdraw consent at any time throughout the course of the study. A signed copy of the ICF will be given to them for their records. The investigator will document the signing of the ICF in the participant's study record. The rights and welfare of the participants will be protected by emphasizing to them that the quality of their medical care will not be adversely affected if they decline to participate in this study.

10.1.2 STUDY DISCONTINUATION AND CLOSURE

This study may be temporarily suspended (paused) or prematurely terminated (halted) if there is sufficient reasonable cause. If the PI prematurely terminates or suspends the study, then the PI will promptly inform study participants (who have not exited study) and the NIH IRB/NECHR in writing, and will provide the reason(s) for the termination or suspension. Study participants will be contacted, as applicable, and be informed of changes to study visit schedule. The study may resume once concerns about safety, protocol compliance, and data quality are addressed.

10.1.3 CONFIDENTIALITY AND PRIVACY

Participant confidentiality and privacy is strictly held in trust by the participating investigators and their staff. This confidentiality is extended to cover testing of biological samples in addition to the clinical information relating to participants. Therefore, the study protocol, documentation, data, and all other information generated will be held in strict confidence. No information concerning the study or the data will be released to any unauthorized third party without prior written approval of the sponsor.

All research activities will be conducted in as private a setting as possible. In the community, privacy screens will be used for interviews, exams, and phlebotomy.

The study monitor, the Office of Clinical Research Policy and Regulatory Operations (OCRPRO) or their authorized representatives, representatives of the IRB, NECHR, or regulatory agencies may inspect all documents and records required to be maintained by the investigator. The clinical study site staff will permit access to all study records.

The study participant's contact information will be securely stored at the NIH-CNM laboratory in Phnom Penh for internal use during the study. ICFs and enrollment logs will be the only links between the unique study identification numbers and participant names. These will be maintained as paper documents at the NIH-CNM lab in locked cabinets. Access will be restricted to those investigators authorized to access identifiable information. At the end of the study, all records will continue to be kept in a secure location for as long a period as dictated by the reviewing IRBs, institutional policies, or sponsor requirements. CRFs, ICFs, and source documents will eventually be transported from the study site to our offices in Phnom Penh, where they will be retained under lock and key by the investigators listed on this protocol and made available for clinical monitoring.

Study participant research data, which are captured on tablets for purposes of statistical analysis and scientific reporting, will be transmitted to and stored on a central server in Phnom Penh and/or LMVR at NIH main campus. This will not include the participant's contact or identifying information. Rather, individual participants and their research data will be identified by a unique study identification number. The study data entry and study management systems used by research staff will be secured and password protected. At the end of the study, the study database will be archived at LMVR in Rockville, MD.

To further protect the privacy of study participants, a Certificate of Confidentiality has been issued by the NIH. This certificate protects identifiable research information from forced disclosure. It allows the investigator and others who have access to research records to refuse to disclose identifying information on research participation in any civil, criminal, administrative, legislative, or other

proceeding, whether at the federal, state, or local level. By protecting researchers and institutions from being compelled to disclose information that would identify research participants, Certificates of Confidentiality help achieve the research objectives and promote participation in studies by helping assure confidentiality and privacy to participants.

10.1.4 FUTURE USE OF STORED SPECIMENS AND DATA

Intended Use: Samples, specimens, and data collected under this protocol may be used to study the following:

- Development of new diagnostic tests to enable more sensitive and specific tests for vector-borne diseases.
- Determination of immune response to vector saliva and vector-borne diseases.
- Determination of incidence and pathogenesis of co-circulating infections (e.g., dengue, JEV, chikungunya, Zika, influenza), as they contribute to this community.
- Development of vaccines and therapeutic interventions to prevent or treat vector-borne infections.
- Isolation or sequencing of viruses (e.g., dengue, chikungunya, Zika), parasites, or bacteria.
- Isolation or sequencing related to host immune response or pharmacogenomics.

Storage: All of the stored study research samples are labeled by a code that only the investigators can link to the subject. Samples are stored at the Malaria Vector and Research Laboratory (CNM-NIH laboratory) at the National Center for Parasitology, Entomology, and Malaria Control, a secure facility with limited access, in Phnom Penh, Cambodia. During the high-volume collection, samples may be temporarily stored in the Kampong Speu District Referral Hospital main laboratory, which is also a secure facility with limited access. In the future, it may be necessary to ship a limited number of samples to Mahidol University when Cambodians go to train and learn the immunoassays in the Thai laboratories. As with previous CNM-NIH collaborative studies, it may be necessary to ship a limited number of samples to NIH for analyses that cannot be performed in Cambodia, and these would be kept in a secure facility at the LMVR in Rockville, MD. However, the purpose is to build laboratory capacity in Cambodia and a priority will be to process as many samples as possible here in the CNM-NIH laboratory. Data will be kept in password-protected computers. Only investigators or their designees will have access to the samples and data.

Tracking: Samples and data acquired under this protocol will be tracked using either Microsoft Excel (for input into the Biological Specimen Inventory) or REDCap.

Disposition:

- In the future, other investigators (both at NIH and outside) may wish to study these samples and/or data for research purposes. If the planned research falls within the category of “human subjects research,” appropriate NIH IRB and NECHR review and approval will be obtained. This includes the NIH or CNM researchers sending out coded and linked samples or data and getting results that they can link back to their subjects.

Loss or Destruction:

- Any loss or unanticipated destruction of samples (for example, due to freezer malfunction) or data (for example, misplacing a printout of data with identifiers) that meets the definition of a reportable event will be reported to the NIH IRB and the NECHR according to NIH Policy 801.

- Additionally, subjects may decide at any point not to have their samples stored. In this case, the PI will destroy all known remaining samples and report what was done to both the subject and to the NIH IRB and NECHR. This decision will not affect the individual's participation in this protocol or any other protocols at NIH.
- However, withdrawal of consent with regard to bio-sample storage may not be possible after the study is completed. If a subject had previously consented to future use and some of their blood has already been used for research purposes, then the information from that research may still be used even after consent is revoked.

